### **5.7 Expected Duration of Trial**

Expected duration of patient participation – Four to six weeks. This will equate to a 2-4 week period between invitation to join study and Study visit 2 when surgery occurs. Study visit 1 will occur a minimum of 2 days prior to surgery. Surgery will not be delayed beyond 31 days from decision to treat the cancer with mastectomy. There will be a 2-3 week period between surgery and the final follow-up Study visit 3, the end of the study will be confirmed as when post-operative histology has been recorded and any plans for re-excision surgery are known.

## 6. Trial Procedures

Assessments	Baseline Visit 1	Surgery Visit 2	Post surgery Visit 3 (2-3 wks post surgery)
Informed consent	X		
Medical history	X		
Pregnancy test (if pre menopausal)	X		
CRF/eCRF completion including data transfer and query resolution	X	X	X
Concomitant medication check	X	X	X
Review/reporting of patient AEs/SAEs		X	X
Place sentimark lesion and ultrasound	X		
Localise lesion during surgery		X	
Check detectability of seed with magnetometer	X	X	
Data collection in theatre		X	
Record migration of clip		X	
Mammogram	X	X	
Mastectomy specimen x-ray		X	

## 7. Assessment of Efficacy

### 7.1 Primary Efficacy Parameters

#### The Primary Endpoint:

An evaluation of the distribution of seed migrations to estimate the risk of markers migrating

- A clinically significant distance (10mm or greater);
- A clinically unsafe distance (40 mm or greater).

Marker (seed) location will be compared radiographically between the post-placement image and the pre-operative image. The position of the marker (seed) will be assessed in relation to anatomical landmarks and any change recorded in mm.

Formally the 95% CI if 0 out of 25 seeds migrate >10mm is 0-13%. However, findings will be considered in conjunction with other observations:

- The observed distribution of migration (e.g. how variable is this distribution and how close does it lie to the limits)
- For any seeds migrating >10mm, a qualitative assessment of underlying characteristics such as haematoma or placement into fatty tissue (both reported as causes of migration in RSL procedures)
- Abnormal tissue responses will be assessed by gross pathology and histology, as part of the safety endpoint.

### 7.2 Secondary Efficacy Parameters

#### Secondary Research Questions:

- Accuracy of initial placement – distance of the marker (seed) on radiographic imaging from the intended site of placement (e.g. lesion, marker clip, calcification);
- Percentage magnetic markers (seeds) within target area;
  - The target area will be detected by mammography on the day of surgery and is defined as within 10mm of the target lesion
- Relationship between depth of marker (seed) and ease of transcutaneous detection;
  - Marker (seed) depth to the nearest skin surface will be estimated sonographically
  - Ease of detection measured by ability to detect the marker (seed) with Sentimag detector and the time to detect marker (seed) in seconds

## 8. Source Data

- Medical records;
- Histopathology reports;
- Specimen x-rays and mammograms;
- CRF.

All documents will be stored safely in confidential conditions. On all study-specific documents, other than the signed consent, the participant will be referred to by the study participant number/code, not by name.

## 9. Assessment of Safety

### 9.1 Specification, Timing and Recording of Safety Parameters.

All Serious Adverse Events (SAEs) will be reported immediately to the Sponsor of the study. Refer to SOP 2a Safety Reporting for clinical trials conducted at UHSM.

European Commission guidance on Medical Devices MEDDEV 2.7/3 Revision 3 May 2015 will be used for reporting all Adverse Events under directives 90/385/EEC and 93/42/EEC.

Serious Adverse Events are defined as:

- Adverse Event that:
  - Led to a death,
  - Led to a serious deterioration in health that either:
    - Resulted in a life-threatening illness or injury, or
    - Resulted in a permanent impairment of a body structure or a body function, or
    - Required in-patient hospitalization or
    - Prolongation of existing hospitalization,
    - Or resulted in medical or surgical intervention to prevent life threatening illness or injury or permanent impairment to a body structure or a body function.
  - Led to foetal distress, foetal death or a congenital abnormality or birth defect

NOTE 1: This includes device deficiencies that might have led to a serious adverse event if a) suitable action had not been taken or b) intervention had not been made

or c) if circumstances had been less fortunate. These are handled under the SAE reporting system.

NOTE 2: A planned hospitalization for pre-existing condition, or a procedure required by the Clinical Investigation Plan, without a serious deterioration in health, is not considered to be a serious adverse event.

### **Device deficiency**

Inadequacy of an investigational medical device related to its identity, quality, durability, reliability, safety or performance. This may include malfunctions, use error, or inadequacy in the information supplied by the manufacturer.

### **Adverse Device Effect (ADE)**

Adverse event related to the use of an investigational medical device.

NOTE 1- This includes any adverse event resulting from insufficiencies or inadequacies in the instructions for use, the deployment, the implantation, the installation, the operation, or any malfunction of the investigational medical device.

### **Serious Adverse Device Effect (SADE)**

Adverse device effect that has resulted in any of the consequences characteristic of a serious adverse event.

### **Unanticipated Serious Adverse Device Effect (USADE)**

Serious adverse device effect which by its nature, incidence, severity or outcome has not been identified in the current version of the risk analysis report.

NOTE: Anticipated SADE (ASADE): an effect which by its nature, incidence, severity or outcome has been previously identified in the risk analysis report

## **REPORTABLE EVENTS UNDER ANNEX 7 AND ANNEX X OF DIRECTIVES 90/385/EEC AND 93/42/EEC RESPECTIVELY**

For the purpose of this guidance and based on the definitions above, the following events are considered reportable events in accordance with Annex 7, section 2.3.5 and Annex X, section 2.3.5 of the above mentioned Directives 5 :

- any SAE,
- any Device Deficiency that might have led to a SAE if:
  - a) suitable action had not been taken or
  - b) intervention had not been made or
  - c) if circumstances had been less fortunate
- new findings/updates in relation to already reported events.

All SAEs and SARs will be reported immediately to the Chief Investigator of the Study, [name], and the Research & Development Office.

Adverse Events requiring reporting:

- Migration of Sentimark magnetic marker (seed) >10mm from cancer location;
- Haematoma following Sentimark placement surgical treatment;
- Sentimark device not resected from breast during cancer surgery.

## **9.2 Procedures for Recording and Reporting Adverse Events**

All Serious Adverse Events (SAEs) should be reported immediately to the Sponsor. The immediate reports should be followed promptly by detailed, written reports using the MEDDEV Summary Reporting Form. The immediate and follow-up reports should identify subjects by unique code numbers assigned to the trial subjects' names, personal identification numbers, and/or addresses.

### **9.2.1 Reporting Timelines**

#### **Report by sponsor to National Competent Authorities (NCA).**

The sponsor must report to the NCAs where the clinical investigation has commenced:

- - for all reportable events as described which indicate an imminent risk of death, serious injury, or serious illness and that requires prompt remedial action for other patients/subjects, users or other persons or a new finding to it: immediately, but not later than 2 calendar days after awareness by sponsor of a new reportable event or of new information in relation with an already reported event.
- - any other reportable events as described or a new finding/update to it: immediately, but not later than 7 calendar days following the date of awareness by the sponsor of the new reportable event or of new information in relation with an already reported event.
- Any other reportable events as described or a new finding/update to the event: immediately, following the date the sponsor becomes aware of the new reportable event or of new information in relation with an already reported event.

### 9.2.2 Causality Assessment

The relationship between the use of the medical device and the occurrence of each adverse event shall be assessed and categorized. During causality assessment activity, clinical judgement shall be used and the relevant documents, such as the Investigator's Brochure, the Clinical Protocol or the risk Analysis Report shall be consulted, as all the foreseeable serious adverse events and the potential risks are listed and assessed there. The presence of confounding factors, such as concomitant medication/treatment, the natural history of the underlying disease, other concurrent illness or risk factors shall also be considered.

The above considerations apply also to the serious adverse events occurring in the comparison group.

For the purpose of harmonising reports, each SAE will be classified according to five different levels of causality. The sponsor and the investigators will use the following definitions to assess the relationship of the serious adverse event to the investigational medical device.

**1) Not related:** relationship to the device or procedures can be excluded when:

- the event is not a known side effect of the product category the device belongs to or of similar devices and procedures;
- the event has no temporal relationship with the use of the investigational device or the procedures;
- the serious event does not follow a known response pattern to the medical device (if the response pattern is previously known) and is biologically implausible;
- the discontinuation of medical device application or the reduction of the level of activation/exposure - when clinically feasible – and reintroduction of its use (or increase of the level of activation/exposure), do not impact on the serious event;
- the event involves a body-site or an organ not expected to be affected by the device or procedure;
- the serious event can be attributed to another cause (e.g. an underlying or concurrent illness/ clinical condition, an effect of another device, drug, treatment or other risk factors);
- the event does not depend on a false result given by the investigational device used for diagnosis 17, when applicable;
- harms to the subject are not clearly due to use error;
- In order to establish the non-relatedness, not all the criteria listed above might be met at the same time, depending on the type of device/procedures and the serious event.

**2) Unlikely:** the relationship with the use of the device seems not relevant and/or the event can be reasonably explained by another cause, but additional information may be obtained.

- 3)** Possible the relationship with the use of the investigational device is weak but cannot be ruled out completely. Alternative causes are also possible (e.g. an underlying or concurrent illness/ clinical condition or/and an effect of another device, drug or treatment). Cases where relatedness cannot be assessed or no information has been obtained should also be classified as possible.
- 4)** Probable the relationship with the use of the investigational device seems relevant and/or the event cannot reasonably be explained by another cause, but additional information may be obtained.
- 5)** Causal relationship: the serious event is associated with the investigational device or with procedures beyond reasonable doubt when:
- the event is a known side effect of the product category the device belongs to or of similar devices and procedures;
  - the event has a temporal relationship with investigational device use/application or procedures;
  - the event involves a body-site or organ that
    - a) the investigational device or procedures are applied to;
    - b) the investigational device or procedures have an effect on;
  - the serious event follows a known response pattern to the medical device (if the response pattern is previously known);
  - the discontinuation of medical device application (or reduction of the level of activation/exposure) and reintroduction of its use (or increase of the level of activation/exposure), impact on the serious event (when clinically feasible);
  - other possible causes (e.g. an underlying or concurrent illness/ clinical condition or/and an effect of another device, drug or treatment) have been adequately ruled out;
  - harm to the subject is due to error in use;
  - the event depends on a false result given by the investigational device used for diagnosis, when applicable;
  - In order to establish the relatedness, not all the criteria listed above might be met at the same time, depending on the type of device/procedures and the serious event. The sponsor and the investigators will distinguish between the serious adverse events related to the investigational device and those related to the procedures (any procedure specific to the clinical investigation). An adverse event can be related both to procedures and the investigational device. Complications of procedures are considered not related if the said procedures would have been applied to the patients also in the absence of investigational device use/application. In some particular cases the event may be not adequately assessed because information is insufficient or contradictory and/or the data cannot be verified or supplemented. The sponsor and the Investigators will make the maximum effort to define and categorize the event and avoid these situations. Where the sponsor

remains uncertain about classifying the serious event, it should not exclude the relatedness and classify the event as “possible”.

Particular attention shall be given to the causality evaluation of unanticipated serious adverse (device) events. The occurrence of unanticipated events related to the use of the device (USADE) could suggest that the clinical investigation places subjects at increased risk of harm than was to be expected beforehand.

### 9.2.3 Reporting Form

The reporting form template for the summary SAE tabulation is given in the Appendix of this document.

The table gives a cumulative overview of the reportable events per clinical investigation and will be updated and transmitted to participating NCAs each time a new reportable event or a new finding to an already reported event is to be reported. More detailed information has to be provided on request of an NCA, if so requested by using the individual reporting form. The sponsor shall identify the new/updated information in the status column of the tabular form featured in the Appendix as:

a = added = new reportable event;

m = modified = new finding/update to an already reported event;

u = unchanged.

Changes in a line should be highlighted in bold and/or colour in the respective column.

The reporting form is study specific and covers only a given clinical investigation, defined by a distinct clinical investigation plan. English is the recommended language for the reporting form. The report should be sent by email in Excel to the participating NCAs, or an equivalent format which allows using the inserted filters. The reporting to MHRA shall use the form template for the summary SAE tabulation as given in the Appendix of MEDDEV 2.7.3 December 2010.

Safety Oversight:

The Trial Steering Committee will meet once all patients have completed the study or earlier if considered necessary by the Chief Investigator. They will consider all Serious adverse events and adverse events and the main safety and efficacy outcomes. Notably they will discuss:

Morbidity and safety of seed placement – recording of any morbidity as a result of Study visit 1 or 2;

Detectability of the seed in the breast. – measured at Study visits 1 and 2 using the hand-held magnetometer;

Assessment of migration of the seed from time of deployment to time of surgery.

Measured on difference in position of magnetic marker (seed) from the cancer

between Study Visits 1 and 2, and assessed on mammograms by a Consultant Radiologist.

If any markers migrate a clinically significant distance, a qualitative assessment will be carried out to see if there is a possible relationship between clinical characteristics seen in patients and movement of the marker. (e.g. Haematoma, placement of seed into fatty rather than soft tissue)

Adverse tissue responses as assessed by gross pathology and histopathology.

#### **9.2.4 Adverse Events that do not require reporting**

n/a

#### **9.3 Urgent safety measures (USMs)**

For any safety issues during the study, refer to SOP 2d Urgent Safety Measures

### **10. Statistics**

#### **10.1 Sample Size**

This protocol has been developed with [name] Medical Statistician at Manchester University.

The sample size has been set at 25 patients to achieve a balance between having sufficient numbers to observe any unexpected patterns of seed migration and keeping to a minimum the number of patients exposed to any risk through participating in the study as no direct benefit is to be expected for participants who consent to taking part in the trial.

RSL seeds are a product similar in size and shape to Sentimark, in widespread clinical use in the same indication, and considered to be safe and effective. In the literature Alderliestenxiii, et al. [2011] report a mean migration of 0.8mm, range 0 to 2.8mm (N=10) for RSL seeds which was considered “clinically negligible” by the authors.

Migration of Sentimark in preclinical studies where the seed is deployed in soft mammary tissue showed a mean migration of 0.95mm, range 0 to 3.6mm (N=10) and no abnormal tissue reaction. Migration observed is substantially similar to that reported by Alderliesten et al for RSL seeds.

From the experience with RSLs, clinically significant migration of radioseeds (greater than 1cm) in larger studies has been reported in 3/456 placements (Grayxiv et al [2004], Sungxv et al [2013]). However when it does occur the reason is often either a pre-existing or newly formed haematoma or placement of the seed into fatty rather than soft tissue.

For this reason, clinical characteristics of patients in whom a seed migrates more than 1cm will be carefully evaluated.

Formally, the 95% CI if 0 out of 25 seeds migrate >10mm is 0-13%. However, findings will be considered in conjunction with other observations including:

- The observed distribution of migration (e.g. how variable is this distribution and how close does it lie to the limits)
- For any seeds migrating >10mm, a qualitative assessment of underlying characteristics such as haematoma or placement into fatty tissue (both reported as causes of migration in RSL procedures)
- Abnormal tissue responses will be assessed by gross pathology and histology, as part of the safety endpoint.

## **10.2 Randomisation**

No randomisation is required.

## **10.3 Analysis**

Simple descriptive summary statistics of the main parameters will be derived together with a graphical presentation of the raw data. Percentages for categorical variables, means, standard deviations, medians and range values for quantitative factors will be calculated as appropriate. 95% confidence intervals will also be presented to provide a measure of accuracy for the estimates.

The relationship between breast size and detectability of the seed by the magnetometer will be assessed using simple correlational analysis.

The statistical software package, SPSS version 22, will be used for the statistical analysis.

Sources of measurement error will be graphically displayed, reviewed and discussed as appropriate.

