#### Methods:

The marker (seed) will be inserted by trained and qualified healthcare professionals under image guidance (ultrasound or radiography) and removed with the surgical mastectomy (breast) specimen.

Sentimark will be placed in the lesion for which a patient is scheduled to have a mastectomy, a minimum of 2 days prior to surgery.

The depth of lesion and marker will be recorded by the radiologist

Confirmation of initial detectability with magnetometer immediately after placement and time to detection (seconds).

Assessment of distance of the magnetic marker (seed) from lesion on pre-operative mammography.

Check mammogram on morning of surgery to ensure Sentimark is still visible.

Surgeon checks that Sentimark can be detected transcutaneously during surgery.

Surgeon performs mastectomy

Record mastectomy weight. 25 patients (range of breast sizes (a minimum of three of each of small (<250g), and medium (250-500g), and five large (>500g) breasts).

Perform pathology assessment of mastectomy tissue and record any unexpected tissue reaction to the Sentimark device (minimum 10 patients)

All adverse events will be recorded from when the patient signs the informed consent until the final study visit.

25 patients

**Trial duration per participant:** 6 weeks maximum

**Estimated total trial duration:** Ten months

**Planned trial sites:** Single – University Hospital of South Manchester

**Total number of participants planned:** 25

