## 4. Trial Objectives and Design

### 4.1. Trial Objectives

Aims of the feasibility study:

- Assess migration of Sentimark magnetic marker (seed) between deployment and surgery;
- Investigate the accuracy of magnetic marker (seed) placement;
- Assess the ability to transcutaneously detect the Sentimark device;
- Examine the safety profile and Adverse Effects of Sentimark device use;
- Explore the relationship between mastectomy weight, depth of lesion and ability to detect the magnetic seed using Sentimag probe;
- Determine marker seed integrity in vivo.

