#### 4.1.1 Primary and Secondary Endpoints/Outcome Measures

The Primary Endpoint:

An evaluation of the distribution of seed migrations to estimate the risk of markers migrating

- A clinically significant distance (10mm or greater);
- A clinically unsafe distance (40 mm or greater).

Marker (seed) location will be compared radiographically between the post-placement image and the pre-operative image. The position of the marker (seed) will be assessed in relation to anatomical landmarks and any change recorded in mm.

Secondary research questions include:

- Accuracy of initial placement – distance of the marker (seed) on radiographic imaging from the intended site of placement (e.g. lesion, marker clip, calcification);
- Percentage magnetic markers (seeds) within target area.
  - The target area will be detected by mammography on the day of surgery and is defined as within 10mm of the target lesion.
- Relationship between depth of marker (seed) and ease of transcutaneous detection;
  - Marker (seed) depth to the nearest skin surface will be estimated sonographically

- Ease of detection measured by ability to detect the marker (seed) with Sentimag detector and the time to detect marker (seed) in seconds

Other Endpoints:

- Safety and tolerability;
  - Tissue responses as assessed by gross pathology and histology will be described
  - Adverse Effects profile will be monitored
- Seed integrity post excision;
- Number of days the marker (seed) was in place;
- Mastectomy weight;
- Relationship between clinical characteristics and movement of the markers --  
If any markers migrate a clinically significant distance, a qualitative assessment will be carried out to see if there is a possible relationship between clinical characteristics seen in patients and movement of the marker. (e.g. Haematoma, placement of seed into fatty rather than soft tissue).

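### Does section 10.3 leave the secondary question on seed depth and ease of detection without an analysis?

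*Combined protocol and SAP*

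**What the plan says.** Section 10.3, repeated in the statistical part of the Summary, names one relationship: "The relationship between breast size and detectability of the seed by the magnetometer will be assessed using simple correlational analysis". The rest of 10.3 is general: descriptive statistics for the main parameters, plots of the raw data, and 95% confidence intervals.

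Section 7.2, matching the Summary and 4.1.1, sets a secondary question: "Relationship between depth of marker (seed) and ease of transcutaneous detection". It defines both sides. For depth: "Marker (seed) depth to the nearest skin surface will be estimated sonographically". For detection: "Ease of detection measured by ability to detect the marker (seed) with Sentimag detector and the time to detect marker (seed) in seconds".

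Section 4.1 has a broader aim: "Explore the relationship between mastectomy weight, depth of lesion and ability to detect the magnetic seed using Sentimag probe". Section 4.1.1 puts "Mastectomy weight" among the other endpoints, below the depth question. The Methods part of the Summary expresses breast size through specimen weight ("Record mastectomy weight. 25 patients (range of breast sizes", followed by weight bands) and also states: "The depth of lesion and marker will be recorded by the radiologist".

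On timing, section 4.2, the schedule in section 6 and the safety oversight text in 9.2.3 place the detectability check at Visits 1 and 2. Section 4.2 puts the depth ultrasound at Visit 1. The Methods text ties seconds to the reading taken straight after placement. At surgery it describes only a check that the seed can be found.

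**The concern.** Read alone, 10.3 seems to analyse the wrong predictor. The secondary question is about depth, and the risk text in section 3 gives a seed lying too deep as the reason detection might fail. Yet the only named correlation uses breast size, a lower-ranked variable. The documents nowhere claim that breast size tracks depth to the nearest skin surface. An analyst who ran only the named correlation could report little or no relationship when depth matters.

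There is also some freedom in the named analysis. Detectability could mean found or not found, or seconds, and there are two visits. The type of coefficient is not given, nor is the handling of an undetected seed, which has no time. These choices could be made after the data are seen, in a study whose results support a CE-mark application.

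**Working it through.** The plan gives no figure for this question, so the check has two parts: what the text already fixes, and how much could turn on what it leaves open.

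**What the text fixes**

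| Item | Where | Settled? |
|---|---|---|
| Depth is to be related to detection | 1, 4.1.1, 7.2 | Yes |
| Definition of depth | 7.2 | Yes: ultrasound, nearest skin surface |
| Visit for depth | 4.2 | Yes: Visit 1 |
| Definition of detection | 7.2 | Yes: found or not, and seconds |
| Visits for detection | 4.2, 6, 9.2.3 | Yes: 1 and 2 |
| Visit for seconds | 1 (Methods) | Tied only to placement, Visit 1 |
| Display and intervals | 10.3 | Yes, in general terms |
| Coefficient for depth; measure and visit for breast size | none | Open |

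Depth and seconds are both tied to Visit 1, so a plot of one against the other is the obvious reading. Lesion depth in 4.1 and seed depth in 7.2 should nearly coincide, because the seed is placed in the lesion.

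**The plan's own interval**

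The one statistical figure in the plan concerns migration: 0 of 25, 95% interval 0 to 13%. With z = 1.96, the Wilson upper limit is z²/(n + z²) = 3.84/28.84 = 13.3%, which agrees. The exact limit is 1 − 0.025^(1/25) = 13.7%. The figure does not bear on depth, but it shows the kind of interval available for a proportion detected. For 25 of 25 the exact lower limit is 0.025^(1/25) = 86.3%.

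**Breast size in place of depth**

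The inputs are assumed: n = 25; depth uniform on 5 to 60 mm; log time = 0.03 × depth plus normal error with SD 0.6; breast size correlated with depth at ρ, with no direct effect on time. The depth-time rank correlation is then about 0.60. A rough product ρ × 0.60 gives 0.18, 0.30 and 0.42 for ρ = 0.3, 0.5 and 0.7. Simulation (20,000 runs per setting) gives:

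| ρ | Size-time correlation | 95% interval excludes 0 |
|---|---|---|
| 0.3 | 0.17 | 12% |
| 0.5 | 0.29 | 28% |
| 0.7 | 0.41 | 53% |
| depth itself | 0.60 | 92% |

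With a depth-time correlation of 0.24, the last column falls to 5%, 8% and 11%, against 20% for depth itself. Breast size is therefore a poor substitute. The table describes a report that leaves depth out, which the plan does not permit. Excluding zero is also not a criterion the plan sets.

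**Choice of measure**

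If every seed is found, a yes/no correlation cannot be computed. The chance of that is p^25: 0.99^25 = 0.78, 0.98^25 = 0.60, 0.95^25 = 0.28, 0.90^25 = 0.07 (p assumed). Seconds would then be the only measure that varies, and the proportion would be reported as 25/25.

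**Undetected seeds**

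In the same assumed setting with about 5 of 25 seeds missed, mostly deep ones, the depth-time correlation of 0.60 becomes 0.54 among detected seeds and 0.71 with missed seeds ranked last. If time is unrelated to depth, ranking missed seeds last turns 0.00 into 0.40, because the result then mixes detection with time.

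**Precision**

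For an observed rank correlation of 0.6 the interval is tanh(atanh 0.6 ± 1.96 × √((1 + 0.6²/2)/22)) = tanh(0.693 ± 0.454), or 0.23 to 0.82. The values 0.54 and 0.71 both lie well inside it.

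**The case for a change.** The strongest case for a change is that the authors evidently thought a relationship needed its own sentence, and wrote one only for breast size. The general text in 10.3 promises summaries and plots but names no measure of association. A sentence would cost almost nothing, since all the data are already planned, and it would close the choice of measure and visit before the data are seen.

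The factual part stands: no method is named for depth, and the breast-size sentence does not state its measure or visit. The inference that the plan goes wrong does not stand. Section 4.1 lists specimen weight and detection as an aim in its own right, and the Summary sets minimum numbers in each breast-size band, so the breast-size correlation has its own purpose and is not offered as an answer on depth. The remaining freedom is narrow: time or yes/no, and which visit's yes/no. The handling of missed seeds can move the estimate, but listing them is natural in a study of 25 patients with raw data plotted. Rank correlation on Visit 1 time among detected seeds would be a sensible choice. It is a preference, since the plan states no method for it to correct.

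**Conclusion.** No change is needed. The plan poses the depth question, defines its variables, schedules their collection, and commits to plots and 95% confidence intervals. It leaves only the coefficient and some details to the analyst, which is an ordinary gap in a descriptive single-arm study of 25 patients. No stated rule produces a wrong answer.

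The loss from using breast size in place of depth could be large (0.60 seen as 0.17 to 0.41), but those figures rest wholly on assumed inputs and on a report that omits a listed secondary question. Done as planned, the analysis is exploratory and imprecise whichever coefficient is used. The primary endpoint, the sample size and the safety oversight are unaffected. This conclusion assumes that the report presents depth against detection and states which measure and visit it used.
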